6.3.9.1 Urine drug screen

As noted above, urine drug screening tests will be performed on all new patients at screening (Visit S1) and for all patients at randomization, Month 12, and anytime during the study, at the discretion of the investigator, to allow appropriate medical management of the patient. For patients enrolling from studies D3820C00005 or D3820C00007, initial urine drug screen information will be obtained from the last visit in these studies. In addition, if, in the opinion of the investigator, a patient is undergoing opiate withdrawal or significant exacerbation of pain, the investigator is to conduct a urine drug screen to rule out non-compliance with the opioid regimen as an explanation for withdrawal or pain. Based on the results of the urine drug screen, clinical picture, and severity of the potential opiate withdrawal symptoms, the investigator will decide if the patient should be discontinued from the study. If the patient tests positive for other illicit drugs, it is up to the investigator to decide after consulting with the study physician, whether these drugs may compromise the patient's ability to comply with study instructions, and whether the patient should be continued in the study.

6.3.9.2 Handling of subjects with elevated liver transaminases

The investigator will be alerted from the central laboratory regarding patients developing ALT or AST >3x ULN during the study, ie, all values above >3x ULN with no upper limit will be alerted. How to handle these patients is described in detail in this section.

All patients with ALT or AST >3x ULN, regardless of whether they stop or continue the intake of study drug, must be closely monitored with repeated laboratory liver tests every third day or more frequently if judged necessary by the investigator until the liver tests begin to improve. Thereafter, liver tests will be performed at an interval decided to be appropriate by the investigator. All patients must be followed until the liver tests have returned to baseline or until a firm explanation (diagnosis) for the elevated liver transaminases has been established.

The specific laboratory tests to be used for confirmation and monitoring include ALT, AST, alkaline phosphatase (ALP), bilirubin (BIL), conjugated BIL, INR, albumin, creatine kinase (CK), Hb, white blood cells (WBC), neutrophils, eosinophils, basophils, lymphocytes, monocytes, sodium, potassium, and creatinine.

Subjects who can continue the intake of study drug

- Patients with ALT or AST $>3x$ ULN but $\leq 8x$ ULN and no clinical signs or symptoms indicating liver dysfunction can, at the discretion of the investigator, continue the intake of study drug with close monitoring.

The patients must be brought back to the study center for an unscheduled visit without any delay, but not later than 72 hours after the test results have been received, for specific evaluation of the underlying cause for the ALT or AST elevation and confirmatory laboratory testing.

A medical history focused on risk factors for liver injury (alcohol consumption, exposure to toxic agents, infections, medications and drug use including herbal remedies, etc) should be obtained, evaluation of recent symptoms (AEs), and physical examination should be done and all relevant information should be captured in appropriate eCRF modules.

Confirmatory laboratory testing should be done and more frequent monitoring of liver tests should be initiated.

Subjects who stop intake of study drug

Patients with the following findings should immediately be contacted and instructed to stop intake of study drug:

- ALT or AST $>8x$ ULN
- ALT or AST $>5x$ ULN for more than 2 weeks
- ALT or AST $>3x$ ULN AND (total bilirubin $>2x$ ULN or INR >1.5). For further instructions on actions to be taken for patients meeting Hy's law criteria, see [Appendix K](#).
- ALT or AST $>3x$ ULN with the appearance of fatigue, nausea, vomiting, right upper quadrant pain or tenderness, fever, rash, and/or eosinophilia ($>5\%$).

Patients must be brought back to the study center for an unscheduled visit without any delay, the next day if possible, but no later than within 72 hours after the test results have been received, for specific evaluation of the underlying cause of the ALT or AST elevation and confirmatory laboratory testing.

A medical history focused on risk factors for liver injury (alcohol consumption, exposure to toxic agents, infections, medications and drug use including herbal remedies, etc) should be obtained, evaluation of recent symptoms (AEs), and physical examination should be done and all relevant information should be captured in appropriate eCRF modules.

Confirmatory laboratory testing should be done and more frequent monitoring of liver tests should be initiated.

In addition, the following blood samples for differential diagnosis purposes should be taken in all patients who stop intake of study drug:

- Alcohol misuse: Carbohydrate deficient transferrin, S-ethanol
- Viral hepatitis: Immunoglobulin M antibody to hepatitis A virus (anti-HAV-IgM), Hepatitis B surface antigen (HBsAg), immunoglobulin M antibody to hepatitis B core antigen (anti-HBc-IgM), antibody to hepatitis C virus (anti-HCV), hepatitis C virus ribonucleic acid (HCV RNA), immunoglobulin M antibody to Epstein Barr virus viral capsid antigen + immunoglobulin G antibody to Epstein Barr virus nuclear antigen (EBV VCA IgM + EBNA IgG, immunoglobulin M antibody to cytomegalovirus (anti-CMV-IgM).
- Autoimmune hepatitis: anti-nuclear antibody, anti-mitochondrial antibody, smooth muscle antibody, immunoglobulin G, immunoglobulin M, immunoglobulin A
- Hereditary disorders: S-Iron and total iron-binding capacity, S-Ferritin, ceruloplasmin, alpha 1-antitrypsin

Imaging techniques and additional examinations can be done if there is a clinical indication as judged by the investigator (eg, ultrasound, computed tomography, liver biopsy). The results of all testing should be entered in the appropriate eCRF modules. It is important that every effort is made to find an explanation for the elevated liver enzymes.

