5.8 Discontinuation from study

Patients are at any time free to discontinue from the study (IP and assessments), without prejudice to further treatment (withdrawal of consent). Such patients will always be asked about the reason(s) and the presence of any AEs. If possible, they will be seen and assessed by an investigator and Visit R15 assessments will be performed. Adverse events will be followed up (see Sections 6.3.4 and 6.3.5); and all study drugs should be returned by the patient.

Discontinued patients will not be replaced.

Patients should be discontinued in the following situations:

- Patient decision. The patient is at any time free to discontinue treatment, without prejudice to further treatment.
- Inadequate pain control after reasonable attempts to control pain have been unsuccessful
- Hepatotoxicity (significantly increased elevations in liver transaminases as defined in Section 6.3.9.2. The protocol for handling patients with elevated liver transaminases including guidelines for discontinuing patients is discussed in Section 6.3.9.2).

- Severe non-compliance to the CSP (including dosing regimen with NKTR-118 or Usual Care, and/or prescribed opioid) as judged by the investigator in consultation with the study physician
- Incorrectly enrolled patients, involving increased safety risk. The investigator should consult with the study physician before discontinuing the patient unless there is a medical urgency.
- Patient is lost to follow-up.
- The patient has a clinically significant or serious AE (eg, new or worsening heart failure) or sustained clinically significant treatment emergent abnormalities in vital signs that would not be consistent with continuation in the study, as determined by the investigator, AstraZeneca, or its representative, or the patient.
- Safety reasons as judged by the investigator.
- Patient becomes pregnant.
- Significantly worsened OIC refractory to medical treatment as judged by the investigator (including failure of the laxative rescue regimen either before or after randomization)
- The patient is unable to comply with the restrictions on the use of concomitant medications as detailed in Section 5.6 (in such cases the investigator should consult with the study physician before discontinuing the patient).
- The patient is unable to tolerate the study drug.

Abdominal pain has been reported as an AE in a previous trial with NKTR-118. The management of severe abdominal pain is discussed in Section 6.3.13.2).

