6.3.2 Definition of adverse events

An AE is the development of an undesirable medical condition or the deterioration/exacerbation of a pre-existing medical condition following or during exposure to a pharmaceutical product, whether or not considered causally related to the product. An undesirable medical condition can be symptoms (eg, nausea, chest pain), signs (eg, tachycardia, enlarged liver), or the abnormal results of an investigation (eg, laboratory findings, ECG). In clinical studies, an AE can include an undesirable medical condition occurring at any time, including run-in or washout periods, even if no study treatment has been administered.

The term AE is used to include both serious and non-serious AEs.

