^e PT/INR is assessed only at screening for new patients in order to calculate Child-Pugh classification. Screening values from studies D3820C00004 or D3820C00005 will be used for patients who participated in these pivotal studies. INR is also to be assessed during the study if patients meet criteria for significant elevation in liver transaminases (See Section 6.3.9.2)

^f If urinalysis is positive for blood, protein, or glucose, microscopic testing is to be conducted.

^g New patients at average risk for CRC who are ≥50 years old (and who have not had a colonoscopy, barium enema, flexible sigmoidoscopy or virtual colonoscopy) will be asked to take a FIT test as indicated in Appendix E. Patients who enroll from studies D3820C00005 or D3820C00007 will not be required to have additional FIT testing

Serum chemistry and hematology tests will be performed for new patients at Visit S1 (screening), and for all patients at randomization, Week 1, Week 2, Months 1, 3, 6, 9, 12, and at follow-up. Total cholesterol will be assessed at randomization, Month 6, and Month 12.

Urine drug screening tests will be performed for new patients at Visit S1 (screening) and for all patients at randomization, Month 12, and anytime during the study, at the discretion of the investigator, to allow appropriate medical management of the patient. Urinalysis will be performed for new patients at Visit S1 (screening) and for all patients at randomization, Month 6, and Month 12. Urine pregnancy tests (for all WOCBP) will be performed for new patients at Visit S1 (screening) and for all patients at randomization, and Month 12. Any positive urine pregnancy test is to be followed up with a serum pregnancy test. Serum pregnancy tests for WOCBP will be performed at Months 1, 3, 6, 9, and the follow-up visit.

For blood volume, see Section 7.1.

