1.1 Identification

In cases of AST or ALT \geq 3x ULN or TBL \geq 2x ULN, please follow the instructions below.

For studies using central laboratories:

- When a subject has an AST or ALT \geq 3xULN **or** TBL \geq 2xULN at any visit, the central laboratory will immediately send an alert to the Investigator (also sent to the AstraZeneca representative)
- If the Quintiles study team or AZ representative are made aware that a local laboratory sample meeting PHL criteria was collected outside of the central laboratory, eg local hospital, the Quintiles study team will:
 - Request the investigative site to conduct a repeat test with the central laboratory
 - Instruct the Investigator to complete the appropriate laboratory CRF modules with the original laboratory test result.

For studies using local laboratories and for laboratory samples collected outside scheduled study visits, eg, at a local hospital the Investigator reviews each laboratory report to identify and notify the Quintiles study team and/or AZ representative when a subject has an increase in AST or ALT \geq 3xULN **or** TBL \geq 2xULN at any visit.

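### Section 6.3.9.2 permits continued dosing of some symptom-free patients whom its own stop list orders off study drug, and it states no precedence

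*Protocol*

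**What the plan says.** Protocol section 6.3.9.2 sorts patients with raised transaminases under two headings.

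**May continue.** Patients with ALT or AST above 3x and up to 8x ULN "and no clinical signs or symptoms indicating liver dysfunction can, at the discretion of the investigator, continue the intake of study drug", under close monitoring. The transaminase range and the absence of clinical signs or symptoms are the only two conditions.

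**Must stop.** "Patients with the following findings should immediately be contacted and instructed to stop intake of study drug". Four findings are listed:

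1. ALT or AST above 8x ULN.
2. ALT or AST above 5x ULN for more than 2 weeks.
3. ALT or AST above 3x ULN together with total bilirubin above 2x ULN or INR above 1.5. This item points to Appendix K: "For further instructions on actions to be taken for patients meeting Hy's law criteria".
4. ALT or AST above 3x ULN "with the appearance of fatigue, nausea, vomiting, right upper quadrant pain or tenderness, fever, rash, and/or eosinophilia" (above 5%).

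Section 5.8 lists this among the situations in which a patient should be discontinued: "Hepatotoxicity (significantly increased elevations in liver transaminases as defined in Section 6.3.9.2". Neither section says which heading governs a patient who fits both.

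**The concern.** The continue rule removes patients above 8x ULN, through its upper limit, and patients with symptoms. It has no condition on duration, bilirubin, INR or eosinophils, and no proviso that the stop findings be absent. A symptom-free patient can therefore satisfy the permission and the stop order together.

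This is a dosing-safety rule to be applied alike at about 130 centers. The overlap includes raised transaminases with raised bilirubin, the combination for which the protocol invokes Hy's law. The heading chosen also changes care. Only patients who stop must have the viral, autoimmune, hereditary and alcohol work-up, and only they are to be recalled on the next day where possible; the 72-hour limit applies to both groups.

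**Working it through.** No sample size, power or error rate is involved, and the plan gives no figure to reproduce. The check is logical: can each stop criterion be true while the continue rule is also met?

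Let x be ALT or AST as a multiple of ULN.

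- Continue: 3 < x ≤ 8 and no clinical signs or symptoms.
- Stop: any of the four findings above.

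| Stop criterion | Excluded by the continue rule? | Overlap in a symptom-free patient |
|---|---|---|
| x > 8 | Yes, by the upper limit of 8 | None |
| x > 5 for more than 2 weeks | No | 5 < x ≤ 8 |
| x > 3 with bilirubin > 2x ULN or INR > 1.5 | No | 3 < x ≤ 8 |
| x > 3 with listed symptoms and/or eosinophilia > 5% | Symptoms yes, eosinophilia no | 3 < x ≤ 8, by eosinophilia alone |

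Six test patients confirm the table. Values not named are unremarkable.

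| Patient | Continue rule met? | Stop rule met? |
|---|---|---|
| 6x for 3 weeks, no symptoms | Yes | Yes, second criterion |
| 4x, bilirubin 2.5x ULN, no symptoms | Yes | Yes, third |
| 4x, INR 1.6, no symptoms | Yes | Yes, third |
| 4x, eosinophils 6%, no symptoms | Yes | Yes, fourth |
| 9x, no symptoms | No | Yes, first |
| 4x with symptoms | No | Yes, fourth |

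The first four fall under both headings; the last two do not.

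**Does the phrase about clinical signs already cover laboratory values?** The protocol's own usage says not. After symptoms, section 6.3.2 lists "signs (eg, tachycardia, enlarged liver), or the abnormal results of an investigation (eg, laboratory findings, ECG") as further, separate categories. Section 6.3.4 likewise treats a laboratory deterioration as something that may or may not come with clinical signs and symptoms. If every laboratory abnormality counted as a clinical sign, the raised transaminase that defines the band could itself disqualify the patient. A narrower reading, in which only bilirubin and INR count as signs of liver dysfunction, would remove the third overlap but leave duration and eosinophilia.

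**With the clause added.** A symptom-free patient may continue only if 3 < x ≤ 8, x has not been above 5 for more than 2 weeks, bilirubin is ≤ 2x ULN, INR is ≤ 1.5 and eosinophils are not above 5%. No patient can then meet both rules.

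**The case against.** The strongest reply is that the rules do not pull in opposite directions. One is a permission and the other an order, so an investigator who stops the patient breaches neither. The stop list is also the more specific text, and section 5.8 supports it. That stands, and it is why the point is minor. It does not remove the contradiction: an investigator who continues at 4x ULN with bilirubin 2.5x ULN is acting within the words of the permission.

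A second reply is that Appendix K protects the bilirubin case. Where ALT or AST reaches 3x ULN or bilirubin reaches 2x ULN "at any visit, the central laboratory will immediately send an alert to the Investigator (also sent to the AstraZeneca representative"), and if both are met the Study Physician agrees the follow-up with the investigator. This is a real safeguard for that case. But Appendix K does not itself order study drug to be stopped, and its criteria do not include INR, duration or eosinophilia.

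A reader might also infer more than the documents support:

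- *That a decision to continue is never revisited.* The stop list is not confined to the first test, and its 2-week criterion makes sense mainly for a patient who was allowed to continue and then retested. All patients above 3x ULN are retested at least every third day until improvement begins, whether or not they stop, and the panel includes bilirubin, INR and eosinophils.
- *That INR and duration fall into a gap because they are unknown at the alert.* Table 2, footnote e, says that "INR is also to be assessed during the study if patients meet criteria for significant elevation in liver transaminases", and the confirmatory panel includes it. Duration can be judged only over time under any wording. This is sequence, not omission.
- *That the alerts in 6.3.9.2 and Appendix K conflict.* They are compatible, and neither needs changing.

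**Conclusion.** The point holds as a narrow internal contradiction. Three of the four stop criteria overlap the symptom-free continue band, and no precedence is stated. The stop list should prevail at any test, so this is wording to correct rather than a missing safeguard, and it belongs at the lowest level of importance.

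The conclusion rests on two readings: that laboratory results are not clinical signs, as sections 6.3.2 and 6.3.4 use the terms; and that the and/or in the fourth criterion lets eosinophilia trigger a stop alone.

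Few patients are likely to be affected, since section 4.2 excludes ALT or AST above 2.5x ULN and bilirubin above 1.2x ULN (unless due to Gilbert's syndrome). The protocol gives no basis for an expected count, and nothing in it supports a claim that harm is probable. The analysis is unaffected.

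**What to change.** In section 6.3.9.2, add to the conditions of the continue rule: *and none of the stopping criteria below is met*.

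This is one clause. It changes no stop limit and adds no test or visit, and Appendix K can stay as it is. It might seem to cost some patients the investigator's discretion to continue, but the stop list already denies that discretion, so nothing is lost.

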6.3.10 Physical examination

A complete physical examination (general appearance, skin, neck, [including thyroid], eyes, ears, nose, throat, chest, lungs, heart, abdomen, back, lymph nodes, extremities, and basic nervous system evaluation) including rectal examination, will be performed for new patients at screening, for patients entering from another study at randomization, and for all patients at Month 6 and Month 12. In addition, at randomization, new patients will have a targeted physical examination (lungs, cardiovascular, abdomen) with weight and optional rectal examination at the discretion of the investigator, if necessary to ensure safety (see Section 3.1.2.1).

For new patients, significant findings that are present prior to the start of study drug (Visit R1) must be included in the Medical History/Current Medical Conditions eCRF page. For patients enrolling from studies D3820C00005 or D3820C00007, significant findings that meet the definition of an AE must be recorded on the AE eCRF. In addition, for all patients, any significant findings made after the start of study drug (Visit R1) that meet the definition of an AE must be recorded on the AE eCRF.

6.3.10.1 CRC Risk Factor Evaluation

New patients must comply with the CRC screening criteria as specified in [Appendix E](#). Patients enrolling from studies D3820C00005 or D3820C00007 will already have complied with these criteria. These criteria are modified from American College of Gastroenterology

Guidelines for Colorectal Cancer (CRC) Screening ([Rex et al 2000](#), [Rex et al 2009](#)) and are intended to make a reasonable and practical good faith effort to rule out underlying colorectal malignancy as a potential contributor to constipation symptoms and to avoid enrolling patients with underlying malignancy into prolonged clinical trials. Patients are classified into high and average CRC risk groups based on their family history. Further division is made based on age, race, and previous diagnostic evaluation for CRC. A FIT test is required for those new patients who are ≥ 50 years of age and at average risk for CRC, unless they provide verification of negative colonoscopy, flexible sigmoidoscopy, barium enema study, or virtual colonoscopy. For more details, please refer to [Appendix E](#).

6.3.11 ECG

6.3.11.1 Resting 12-lead ECG

Digital ECGs (dECG) for all patients at all centers will be conducted at the center using a machine provided by the central ECG laboratory and will be transmitted to the central ECG laboratory. The ECG machine will also print off 2 copies of the ECG by default, 1 copy that can be provided to the central ECG laboratory for digitization and analysis if necessary. Digital ECGs will be performed for new patients at screening, and for all patients at randomization, and all study visits after randomization. Digital ECGs will be obtained after the patient has been resting in a supine position for at least 10 minutes. A single 12-lead ECG will be obtained for new patients at Screening (Visit S1) and for all patients at the follow-up visit. Triplicate ECGs will be performed for all patients at the randomization visit (Visit R1, pre-dose/as an initial assessment and 2 hours post-dose/after initial assessments have been completed), and at all other study visits during which ECGs are collected (Week 1, Week 2, Months 1, 3, 6, 9, and 12). After the patient has been supine for at least 10 minutes, 3 standard 12-lead dECG recordings will be performed within a 5-minute period while the patient remains supine.

All dECGs will be documented by recording date, time, heart rate, QRS duration, PR interval, RR interval, QT, and QTcF. QTcF intervals will be calculated using the Fridericia formula ([Puddu et al 1988](#)).

If indicated, additional ECG assessments can be made at the discretion of the investigator. These assessments should be entered as an unscheduled assessment on the appropriate eCRF.

The investigator will judge the overall interpretation as normal or abnormal. If abnormal, it will be decided as to whether or not the abnormality is clinically significant or not clinically significant and the reason for the abnormality will be recorded on the eCRF, if the investigator considers it clinically significant. Abnormal values shall not be recorded as AEs unless deemed clinically significant.

Quality assurance of the ECG waveform and patient demographics will be conducted by a central ECG laboratory operator. Digital ECGs will be processed through a computer interpretation program and then reviewed, first by an ECG analyst and then by a board-certified cardiologist. Electrocardiogram reports will be provided to the study sites (preferably by email although fax is possible) once the analysis is complete.

It is the investigator's judgment whether the findings/results on the central ECG laboratory report are clinically relevant or not and whether the findings will result in the discontinuation of the patient from the study based on the I/E or discontinuation criteria.

